1.0 Background

Diabetes is a leading cause of kidney failure, heart disease, stroke, visual impairment, and non-traumatic lower limb amputations. Diabetes self-management can prevent or delay many diabetes-related complications, yet patients struggle to consistently engage in recommended self-care behaviors. Patient activation (i.e., knowledge, skills and confidence to manage their own health and care) is essential to achieving optimal diabetes self-management and is associated with lower costs.

By providing an engaging and convenient means to track and visualize health data, obtain education and guidance, and connect patients and doctors, patient portals offer a promising platform to increase patient activation, enhance care and promote self-management while overcoming the limitations of costly and difficult to scale face-to-face interventions. We recently applied user-centered design sprint methodology and key strategies for patient engagement to develop a patient web portal intervention for patients with diabetes called the My Diabetes Care (MDC; formerly Diabetes Dashboard).

MDC is embedded within an established patient portal, My Health at Vanderbilt (MHAV). MDC is a multi-faceted intervention designed to help patients better understand their diabetes health data as well as support self-management. The MDC uses infographics to visualize and summarize patients' diabetes health data, incorporates motivational strategies (e.g., social comparisons), and provides literacy-level appropriate educational resources. MDC is grounded in a well-established Chronic Care Model (CCM) adapted for eHealth (i.e., healthcare practices supported by electronic processes and communication). By leveraging elements within the Model's five domains (self-management support, delivery system design, decision support, clinical information systems, and eHealth education), MDC has the potential to create more informed and activated patients leading to improved outcomes.

2.0 Rationale and Specific Aims

This study aims to evaluate the effects of MDC on patient activation in adult patients with type 2 diabetes mellitus (T2DM). In addition, we plan to explore secondary outcomes, including system use and usability, and the effects of MDC on diabetes self-efficacy, knowledge, self-care, medication adherence, distress, and clinical endpoints. The study will serve as a pilot for a larger definitive trial evaluating the effect of MDC on clinical endpoints. We will recruit patients into two study arms which will receive: (1) usual care arm and (2) the intervention arm. Participants in Arm 1 (usual care) will have access to the standard version of My Health at Vanderbilt (MHAV), the Vanderbilt patient portal. Participants in Arm 2 will be provided access to a version of MHAV embedded with the intervention, MDC. Participants in both arms will be told the purpose of the study is *to determine satisfaction with two versions of MHAV among patients with diabetes*. The study will utilize questionnaires to quantify participants' responses to MDC in comparison to usual care. Each participant will be enrolled in the study for six months.

3.0 Inclusion/Exclusion Criteria

Participants will be eligible for the study if they are a patient at one of the 14 participating VUMC-affiliated adult primary care clinics and have T2DM, are currently being treated with at least one diabetes medication, are able to speak and read in English, are age 21 or over, have an existing MHAV account, and have reliable access to a desktop or laptop computer with internet access.

We will exclude patients living in long term care facilities, patients with known cognitive deficits, patients with severe visual impairment, and patients currently participating in another diabetes related research study.

4.0 Enrollment/Randomization

Participants will be able to complete an electronic consent form and enroll online via Research Electronic Data Capture (REDCap™) version 5.0.8. The study coordinator will verify all eligibility criteria prior to randomization. The procedure and risks will be explained to the participants and the consent form signed as per standard practice. All participants are randomly assigned to one of two groups: (1) intervention group which will have access to a version of MHAV embedded with the MDC or (2) usual care group which will have access to the currently available version of MHAV. Participants randomized to the intervention are advised to view MDC on a desktop or laptop device because the present version of MDC is not mobile friendly. The randomization sequence will be generated by the research team biostatistician using a permuted block randomization scheme stratified by clinic site and participants' age group (age 65 and over vs under 65). The randomized assignment for eligible participants will be accessible to the study coordinator and biostatistician using the Research Electronic Data Capture (REDCap™) Randomization Module. Once a randomization assignment is provided, the participant will be entered into the study and will be included in an intention to treat analysis in accordance with the CONSORT guidelines. Our target enrollment is 300 participants (150 per arm).

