5.0 Study Procedures

Setting. Participants will be recruited from 14 VUMC-affiliate adult primary care clinics located throughout Middle Tennessee (4 urban, 10 suburban). An EHR (Epic Systems Corp.) stores all clinical data and patients receive access to their clinical data via an integrated and highly-adopted patient web portal, MHAV.

Participants and Recruitment. On a rolling basis, potentially eligible patients will be selected from a randomly ordered list of established adult patients with diabetes from participating clinic sites and sent a recruitment letter describing the study. In addition, we will use My Research at Vanderbilt to send the recruitment letter to current patient portal users who elected to allow investigators to contact them about research opportunities via email. Interested patients can contact a research assistant to learn more about the study. To enroll, participants will complete a web-based study eligibility screener and electronic consent form on the web via REDCap (Research Electronic Data Capture) version 5.0.8.

Intervention and Control. Participants randomized to the intervention arm will be provided access to a version of MHAV embedded with the MDC viewable on a desktop or laptop device (MDC is not currently available on mobile devices). MDC includes infographics to visualize and summarize patients' health data, incorporates motivational strategies (e.g., social comparisons and gamification), provides literacy-level appropriate educational resources, and contains secure-messaging capability. Participants randomized to the usual care arm will have access to the currently available version of MHAV that includes the ability for patients to review pertinent health data, review medical information about their conditions, and communicate with their health care team.

Data Collection and Outcome Measures. Study participants will complete questionnaires electronically via email using REDCap™ at three time points: enrollment (T_0), three-month follow-up (T_1), and six-month follow-up (T_2). Enrolled participants will be asked to provide information on the following covariates: socioeconomic status, marital status, race/ethnicity, education level, and health literacy.

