6.0 Statistical Analysis Plan

The study is designed to evaluate the effects of MDC on patient activation (primary analysis) and explore the effects on other secondary cognitive and behavioral outcomes relative to the control group. We will use a t-test to compare the change in PAM score between the MDC and control groups. If the normality assumption is violated, the non-parametric Wilcoxon rank sum test will be used. We will use mixed-effects regression models to estimate the intervention effects across time while adjusting for the baseline measure of the outcome. Nonlinear associations will be modeled with regression splines. The mixed-effects model will use fixed effects for patient-level characteristics and random effects for health care provider variables. We will provide point estimates with CIs and graphically depict our results. If necessary, multiple imputation will be used to impute the missing values. The analysis with multiple imputation assumes missing at random (i.e., the model properly handles missing data by including covariates associated with reasons for dropout). The characteristics of participants who do not complete the study or do not comply with the treatment will be compared for both

conditions. Independent t-tests or if appropriate, Wilcoxon rank sum tests will be used to compare change in secondary outcomes between the MCD and control groups. Mixed-effect models will also be used to evaluate the effects of MDC on secondary outcomes across time.

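### Randomisation is stratified by 14 clinics and by age group, but the primary t-test and its Wilcoxon fallback ignore both factors and the mixed model names neither; if they predict change in PAM, the t-test's standard error is too large.

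*Combined protocol and SAP*

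**What the plan says.** Section 4.0 (Enrollment/Randomization) generates the allocation "using a permuted block randomization scheme stratified by clinic site" and by age group, 65 and over against younger. Section 3.0 requires participants to be patients at "one of the 14 participating VUMC-affiliated adult primary care clinics", so there are 14 × 2 = 28 strata for a target of 300 participants, 150 per arm. The block size is not stated.

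Section 6.0 (Statistical Analysis Plan) gives the primary comparison: "We will use a t-test to compare the change in PAM score between the MDC and control groups". The fallback is: "If the normality assumption is violated, the non-parametric Wilcoxon rank sum test will be used". For the other outcomes, "Independent t-tests or if appropriate, Wilcoxon rank sum tests will be used to compare change in secondary outcomes". None of these tests carries a stratum term.

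Section 6.0 also plans a mixed model that adjusts for the baseline value of the outcome, with "fixed effects for patient-level characteristics and random effects for health care provider variables". Clinic and age group are not named there, nor in the list of covariates to be collected in section 5.0. Nothing in the document commits either factor to any analysis.

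**The concern.** Permuted blocks within strata force the arms to be nearly balanced on clinic and age group. Variation between strata therefore largely cancels out of the difference in means. An ordinary two-sample t-test does not know this and still counts that variation in its standard error. The Wilcoxon test does the equivalent through its null variance.

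If the two factors predict change in PAM, the confidence interval is wider than the design warrants and the test rejects a true null less often than its nominal level. The sponsor would have taken the trouble to stratify and then not used the benefit. Precision matters here because section 2.0 presents the study as a pilot for a larger definitive trial.

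There is also a pre-specification gap. The mixed model could include both factors, but as worded this can be decided after the data are seen.

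**Working it through.** **No figure in the plan to reproduce.** The target of 300 is given without alpha, power, effect size, SD or dropout. I assume a two-sided 5% level and work in SD units of the change score.

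**Inputs from the documents:** 14 clinics, 2 age groups, 300 participants allocated 1:1. That is 28 strata and 300/28 = 10.7 participants per stratum.

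**Assumption:** R2, the share of variance in change in PAM explained by clinic and age group, is not given. I use 0 to 15%.

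**Formulas** (near-perfect balance within strata, no dropout), with k = sqrt(1 − R2):
- t-test's reported SE = sqrt(4/300) = 0.1155; true SE = k × 0.1155; ratio = 1/k.
- Actual type I error of the t-test = 2 × (1 − Phi(1.96/k)).
- Effect giving 80% power at R2 = 0: d = (1.960 + 0.842) × 0.1155 = 0.3235 SD.
- Power of the t-test = 1 − Phi((1.96 × 0.1155 − d)/(k × 0.1155)).
- Power of the adjusted analysis = 1 − Phi(1.96 − d/(k × 0.1155)).
- N at which the t-test matches the adjusted power = 4 × (sqrt(75) + 1.96 × (1 − k)/d)^2.

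| R2 | SE ratio | t-test type I error | Power, t-test | Power, adjusted | N to match |
|---|---|---|---|---|---|
| 0 | 1.000 | 5.0% | 80.0% | 80.0% | 300 |
| 2% | 1.010 | 4.8% | 80.2% | 80.8% | 304 |
| 5% | 1.026 | 4.4% | 80.6% | 82.0% | 311 |
| 10% | 1.054 | 3.9% | 81.3% | 84.0% | 322 |
| 15% | 1.085 | 3.4% | 81.9% | 86.0% | 334 |

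**Do small strata and incomplete blocks remove the effect?** Simulation with 10,000 trials per setting; assumed blocks of 4, unequal clinics, 40% aged 65 and over, and R2 split equally between the two factors. Monte Carlo error is about 0.2 points for type I error and 0.4 for power. The adjusted analysis is a linear model with clinic and age group as main effects.

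| R2 | Type I error, t-test | Type I error, Wilcoxon | Power, t-test vs adjusted |
|---|---|---|---|
| 0 | 4.8% | 4.9% | 79.7 vs 79.4% |
| 2% | 4.8% | 4.6% | 80.4 vs 80.8% |
| 5% | 4.6% | 4.6% | 79.1 vs 80.6% |
| 10% | 4.1% | 4.1% | 80.6 vs 83.4% |
| 15% | 3.4% | 3.4% | 81.4 vs 85.5% |

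The adjusted analysis held its type I error at 4.8% to 5.2%. The t-test's reported against empirical SE was 0.1154 against 0.1111 at R2 = 10% (ratio 1.039) and 0.1155 against 0.1076 at 15% (ratio 1.073). The effect is somewhat milder than the formula gives, but it remains.

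**Sensitivity to block size.** A separate simulation (4,000 trials per setting) at R2 = 10% gave SE ratios of 1.067, 1.042 and 1.046 for blocks of 2, 4 and 6.

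**Sensitivity to dropout.** With 20% random dropout (assumed), the t-test's type I error was 5.0, 4.9, 4.3, 4.2 and 3.9% at R2 = 0, 2, 5, 10 and 15%. Power, t-test vs adjusted, was 69.7 vs 69.2% (R2 = 0), 70.8 vs 70.7% (2%), 71.1 vs 72.2% (5%) and 70.9 vs 74.1% (10%).

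**The case against.** The strongest objection is that R2 may be close to zero. The outcome is a within-person change, which already removes stable differences in level between clinics and age groups. With 40% aged 65 and over and R2 split equally, the gap between age groups in change in PAM would have to be sqrt((R2/2)/0.24): 0.32 SD at R2 = 5% and 0.46 SD at 10%. The first equals the treatment effect that 300 participants can detect with 80% power, and the second exceeds it. Nothing in the documents supports gaps of that size. This stands. It is why the point concerns modest efficiency and why the size is conditional on R2.

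A related objection is that at R2 = 5% the inflation may not be visible: in the 4,000-trial simulation with blocks of 4, the t-test's reported SE was 0.995 of the empirical value. That is simulation noise. In the same run the adjusted SE was 0.973 of its empirical value, although it is correct in theory, so the empirical spread ran high by chance. Comparing the two reported SEs directly gives 0.1153/0.1126 = 1.024, close to the formula's 1.026.

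Third, the mixed model may already cover the factors. Age is a patient-level characteristic, and provider effects could absorb part or all of clinic. This also stands for the model: whether its standard error is affected depends on what is finally included. It does not help the t-test or the Wilcoxon test, which come first in section 6.0.

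Finally, the error is conservative and no power target is stated, so nothing documented is missed. That is correct and limits the weight of the point, but it is no reason to leave out a change that costs almost nothing.

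**Conclusion.** The point holds. The analysis does not follow the randomisation: the t-test and Wilcoxon test ignore both stratification factors, and no model commits to them. The claim about the standard error is firm for the t-test, with the analogous effect on the Wilcoxon test. For the mixed model the defect is unspecific wording.

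Validity is not at risk. The treatment estimate is unbiased and type I error can only fall below its nominal level. The size depends on an R2 that the documents do not give. At 2% or less the loss is negligible. At 5% to 10% the t-test's standard error is up to about 3% to 5% too large and about 1 to 3 points of power are lost, equivalent to roughly 11 to 22 extra participants by formula. These figures assume a two-sided 5% level, 1:1 allocation and an effect of 0.3235 SD.

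**What to change.** State in section 6.0 that the primary analysis of PAM is a baseline-adjusted model with arm, baseline PAM, age group (65 and over against younger) as a fixed effect, and clinic as a fixed or random intercept. Name the same two terms in the models for the secondary outcomes. Section 6.0 already plans a baseline-adjusted mixed model, so this makes an existing analysis specific and moves it to first place. The gains shown above are for clinic and age group alone; any effect of the baseline term is separate and not quantified here.

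Use main effects, 13 + 1 = 14 degrees of freedom, rather than 28 cells of about 11 participants. Keep the t-test or Wilcoxon test as a supporting analysis if wanted. If a rank-based test is kept as a fallback, a stratified version (van Elteren) would respect the design.

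The cost is wording, fixed before outcome data are seen. Both factors are known at randomisation, so no new data are needed. If they predict nothing, adjustment costs about 0.3 points of power without dropout and 0.5 to 1.0 points with an assumed 20% dropout.

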5.0 Study Procedures

Setting. Participants will be recruited from 14 VUMC-affiliate adult primary care clinics located throughout Middle Tennessee (4 urban, 10 suburban). An EHR (Epic Systems Corp.) stores all clinical data and patients receive access to their clinical data via an integrated and highly-adopted patient web portal, MHAV.

Participants and Recruitment. On a rolling basis, potentially eligible patients will be selected from a randomly ordered list of established adult patients with diabetes from participating clinic sites and sent a recruitment letter describing the study. In addition, we will use My Research at Vanderbilt to send the recruitment letter to current patient portal users who elected to allow investigators to contact them about research opportunities via email. Interested patients can contact a research assistant to learn more about the study. To enroll, participants will complete a web-based study eligibility screener and electronic consent form on the web via REDCap (Research Electronic Data Capture) version 5.0.8.

Intervention and Control. Participants randomized to the intervention arm will be provided access to a version of MHAV embedded with the MDC viewable on a desktop or laptop device (MDC is not currently available on mobile devices). MDC includes infographics to visualize and summarize patients' health data, incorporates motivational strategies (e.g., social comparisons and gamification), provides literacy-level appropriate educational resources, and contains secure-messaging capability. Participants randomized to the usual care arm will have access to the currently available version of MHAV that includes the ability for patients to review pertinent health data, review medical information about their conditions, and communicate with their health care team.

Data Collection and Outcome Measures. Study participants will complete questionnaires electronically via email using REDCap™ at three time points: enrollment (T_0), three-month follow-up (T_1), and six-month follow-up (T_2). Enrolled participants will be asked to provide information on the following covariates: socioeconomic status, marital status, race/ethnicity, education level, and health literacy.

The primary outcome measure will be change in patient activation as assessed by the Patient Activation Measure (PAM-13). Secondary intermediate outcomes include diabetes self-efficacy, diabetes knowledge, diabetes distress, diabetes self-care, system usability/satisfaction, and system usage. Additional secondary outcome such as blood glucose control, blood pressure control, cholesterol control, and flu vaccination status will also be assessed by EHR abstraction. To ensure the fidelity of the intervention, monthly quality assurance checks will be used to ensure the MDC is functioning correctly (e.g., displaying data correctly).

Based on pilot testing, we estimate time to completion for questionnaires to be about 25 minutes at T_0 and about 20 minutes at T_1 and T_2 . Participants will be compensated \$40 for completing the enrollment questionnaire (T_0) and \$35 each for completing the three-month (T_1) and six-month (T_2) follow-up questionnaires.

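### The likely primary analysis is an unadjusted t-test on PAM-13 change, at a visit and alpha not stated; a baseline-adjusted comparison at one named visit would be at least as precise at no extra cost.

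*Combined protocol and SAP*

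**What the plan says.** Section 5.0 defines the endpoint: "The primary outcome measure will be change in patient activation as assessed by the Patient Activation Measure (PAM-13"). It schedules questionnaires at "enrollment (T_0), three-month follow-up (T_1), and six-month follow-up (T_2"). It does not list PAM-13 by visit. That PAM-13 is asked at both follow-ups is an inference, supported by the equal questionnaire length at the two follow-ups ("about 25 minutes at T_0 and about 20 minutes at T_1 and T_2") and by the plan to model effects over time.

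Section 6.0 opens with "The study is designed to evaluate the effects of MDC on patient activation (primary analysis"), which attaches the label to patient activation and not to a test. It then says "We will use a t-test to compare the change in PAM score between the MDC and control groups", followed by "If the normality assumption is violated, the non-parametric Wilcoxon rank sum test will be used", with no criterion for a violation. Next comes "We will use mixed-effects regression models to estimate the intervention effects across time while adjusting for the baseline measure of the outcome", without a named contrast or visit. On the model's structure it says "The mixed-effects model will use fixed effects for patient-level characteristics and random effects for health care provider variables". Confidence intervals are promised without a level. No alpha, sidedness or power is given anywhere. Section 4.0 sets the target at 300 participants, 150 per arm, with randomization stratified by clinic site and age group.

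**The concern.** The t-test comes straight after the primary-analysis label and uses the outcome as section 5.0 defines it, so most readers would take it as primary. A change score subtracts the whole baseline value. That is the best use of baseline only when the regression slope of follow-up on baseline equals 1. Otherwise it carries baseline noise that adjustment would remove. The sponsor already collects the baseline score and already intends to adjust for it elsewhere, so the primary comparison may give up precision for nothing in return.

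The second matter is definition. If PAM-13 is measured at both follow-ups, two different changes fit the wording. Should the three- and six-month results disagree, the plan does not say whether the trial met its aim on patient activation. Section 2.0 describes the study as a pilot for a larger trial on clinical endpoints, which lowers the stakes, but the plan still names a primary outcome and enrols 300 people to assess it.

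**Working it through.** **The plan's own figure.** The 150 per arm in section 4.0 cannot be reproduced, because no alpha, power, effect size or SD is given. It is used below only as a reference size.

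**Inputs.** From the documents: 150 per arm, a baseline and two follow-up questionnaires. Assumed: two-sided 5%, complete data, baseline to follow-up correlation r from 0.3 to 0.8, and follow-up SD equal to k times baseline SD, with k = 0.8, 1 or 1.25.

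**Step 1: precision at one visit, equal SDs.** In units of the common variance, the change score has variance 2(1 − r) and the baseline-adjusted outcome has variance 1 − r². Their ratio is (1 + r)/2. The SE ratio is its square root, and the t-test needs 150 ÷ ((1 + r)/2) per arm to match 150 adjusted.

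| r | variance ratio | SE ratio | t-test n per arm to match 150 adjusted |
|---|---|---|---|
| 0.3 | 0.65 | 0.806 | 231 |
| 0.5 | 0.75 | 0.866 | 200 |
| 0.7 | 0.85 | 0.922 | 176 |
| 0.8 | 0.90 | 0.949 | 167 |

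In power terms, for a true difference of 0.3 SD with 150 per arm, the t-test gives 73.8% and the adjusted analysis 85.1% at r = 0.5. At r = 0.7 the figures are 91.8% and 95.3%.

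**Step 2: unequal SDs.** The SE ratio becomes √[k²(1 − r²) / (1 + k² − 2rk)].

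- k = 0.8, r = 0.3: √(0.5824 / 1.16) = 0.71.
- k = 0.8, r = 0.8: √(0.2304 / 0.36) = 0.80.
- k = 1.25, r = 0.3: √(1.4219 / 1.8125) = 0.89.
- k = 1.25, r = 0.8: √(0.5625 / 0.5625) = 1.00.

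The denominator equals k²(1 − r²) + (1 − rk)², so the ratio cannot exceed 1. It equals 1 only when the slope rk is 1, as in the last line. The remaining cost of adjustment is one degree of freedom.

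**Step 3: the open visit.** Suppose the t-test is primary and a significant result at either visit could be claimed. With follow-ups correlated s with each other, the two change scores correlate (1 − 2rk + sk²) / (1 + k² − 2rk). At k = 1:

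- r = s, any value: correlation 0.5, false-positive rate 9.1%.
- r = 0.5, s = 0.8: correlation 0.8, rate 7.8%.
- r = 0.3, s = 0.8: correlation 1.2/1.4 = 0.857, rate 7.4%.

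With k = 0.8 or 1.25 and s = 0.8 the range is 7.1 to 9.2%. With one visit named, the rate is 5%.

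**The case against.** The strongest reply is that a change-score t-test in a randomised trial is valid and matches the outcome as defined, so naming the visit and alpha would settle the ambiguity and adjustment is only a preference. Validity is not in dispute. What stands against the reply is that the adjustment uses data already collected and a method already planned, and cannot lose more than one degree of freedom.

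Three parts of the case against do stand. First, the gain is conditional, since it disappears when the slope is 1. Second, the mixed model in section 6.0 has unlisted patient characteristics, splines and provider effects. Making that model primary as written would open more choices than the t-test has, and the figures above do not describe it. The fix therefore has to be a simple model. Third, six-month enrolment in section 2.0 hints at the six-month visit, although nothing ties it to the outcome.

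A reader might infer that the t-test, the Wilcoxon test and the mixed model compete on equal terms, with false-positive rates well above 10%. The documents do not support that. The natural reading makes the t-test primary, and no text allows any significant result to be claimed. A reader might also infer that the switch to Wilcoxon inflates error. In simulation with an assumed normality check, it moved the either-visit rate by at most about half a percentage point. What remains is that the data decide whether a mean difference or a rank-based quantity is tested.

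**Conclusion.** The concern holds as an improvement that SAP wording alone can deliver, together with a gap in definition. The missing visit and alpha are plain from the text. The precision gain is algebraic in direction, but its size rests on assumed correlations and SDs: an SE ratio of 0.81 to 0.95 with equal SDs and r from 0.3 to 0.8, widening to 0.71 to 1.00 when follow-up SD is 0.8 or 1.25 times baseline SD. The either-visit false-positive rate of about 7 to 9% is secondary. It applies only if the visit stays open and either result may be claimed, which the plan neither permits nor rules out. This should be changed, but it does not make the planned analysis invalid.

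**What to change.** Before unblinded data are seen, state in the SAP:

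1. One primary visit, which is the sponsor's choice; six months fits the enrolment period.
2. Two-sided 5%, with a 95% CI.
3. As primary analysis, the between-arm mean difference in PAM-13 at that visit from a linear model with arm and baseline PAM. The stratification factors, clinic and age group, may be added; no other covariates.
4. If both follow-ups enter one model, a within-patient correlation term, because section 6.0 names random effects only for provider variables.
5. The change-score t-test, the Wilcoxon test, the other visit and the fuller mixed model as supportive, with the primary analysis kept whatever the distribution.

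This costs wording only, with no extra patients or data. There are two downsides. An effect seen only at the other visit could not be claimed as primary. A mean-based test can also lose power if scores are clearly non-normal: for a pure shift of 0.3 SD with 150 per arm, simulated t-test against Wilcoxon power is 73 against 71% for normal data, 74 against 80% at skewness 1, and 74 against 97% at skewness 2. A sponsor who expects marked skewness could name the rank test in advance instead.
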